6.3 Data Elements

Data elements and sources are described below and in Table 2.

6.3.1. Facility-level data: Facility-level data are needed for facility recruitment, randomization, and descriptive purposes. Organizational data from OSCAR include: number of beds, for-profit status, and NH chain. Aggregated MDS data at Brown University provide information case-mix (% long-stay and post-acute care patients). MDS data are also used to calculate the hospitalization rate of each facility by estimating the number of patient days at risk of hospitalization from the nursing home and counting the number of actual hospital transfers to hospital per unit time. It is these hospital specific rates from the prior year which will be used to undertake the stratified randomization scheme (*see Section 4.4.2*). Medicare claims available at Brown University will be used to determine the facilities' hospitalization rates for the subset of patients with Medicare fee for service.

| Table 2: Data Element and Sources | | | | | |
|--|---|---------------|------------|-----------------|--------------|
| Data Element | Purpose | SOURCE | | | |
| | | EMR | MDS | Medicare | OSCAR |
| Facility-Level | | | | | |
| Organization | recruitment | | | | X |
| Case-mix | recruitment | | X | | |
| Prior Hospitalization rate | randomization | | X | | |
| | | | | | |
| Patient-Level | | | | | |
| Demographic | covariate | X | X | | |
| Long vs. short-stay | Cohort definition | | X | | |
| Functional status | target sub-population identification, covariate | | X | | |
| Cognitive status | target sub-population identification, covariate | | X | | |
| Medical condition | target sub-population identification, covariate | X | X | | |
| Insurance | covariate | | | X | |
| Advance directives | 2° outcome | X | | | |
| Health services use | 1° and 2° outcome | X | X | X | |
| Burdensome interventions | 2° outcome | X | X | X | |
| Death | description, competing risk | | X | X | |
| Intervention implementation | monitoring fidelity | X | | | |

6.3.2. Patient-level data:

6.3.2.a. Cohort description, identification of target sub-groups, and other independent variables

Demographic data: From MDS: Age, gender, race, ethnicity, religion, primary language, marital status, and length of NH stay.

Long-stay or new admission to post-acute care: From MDS.

Functional status: From MDS: Ability to perform specific activities of daily living ADLs (as required for cohort identification (i.e., feeding, transferring, ambulation) and validated ADL summary scale (range, 7-28).

Cognitive status: From MDS: Ability for daily decision-making and Brief Interview for Mental Status (BIMS).⁸⁷

Medical conditions: From MDS: Dementia, CHF, COPD and all other active medical diagnoses.

Insurance status: Medicare Enrollment file: Traditional Medicare Fee-for-Service or Medicare Advantage, Medicaid.

6.3.2.b. Outcomes

Advance directives: From EMR: DNR, do-not intubate (DNI), DNH, no feeding tubes, no artificial hydration.

Health services utilization: From Medicare claims and EMR/MDS (for patients not in traditional Medicare fee-for-service): i. hospital transfers, and ii. hospice.

Burdensome interventions: From Medicare claims and EMR/MDS: Feeding tube insertion, intubation, intravenous therapy.

Death: From Medicare Vital Status files: Date of death

Intervention implementation: EMR: Video Status Report User Defined Assessment.

7. SAFETY ASSESSMENTS

7.1. Minimal Risk Determination

We will seek a minimal risk determination for the PROVEN trial as per HHS 45 CFR 46.102: “*Minimal risk means that the probability and magnitude of harm or discomfort anticipated in the research are not greater in and of themselves than those ordinarily encountered in daily life or during the performance of routine physical or psychological examinations or tests.*”

Justification for a minimal risk determination is based on several considerations. First, all NHs must engage patients and families in ACP as part of routine clinical practice. There is currently no standardized method by which NHs conduct ACP. PROVEN will compare a practice intervention (rolled out in intervention sites as standard operating procedures as directed by corporate leadership) that uses videos to enrich ongoing ACP practices. Prior studies evaluating the ACP videos by our group included several hundred subjects, including healthy older adults, NH patients, family members of patients with life-limiting illnesses and patients with advanced cancer and congestive heart failure.^{66, 67, 70-72, 125} The videos were also tested in our UH2 pilot study. Finally, the videos have been seen by thousands of patients in Hawaii as part of an on-going state-wide implementation program. In prior research, our pilot testing, and Hawaii initiative, there were no instances of untoward viewer distress and the videos never had to be stopped because of adverse viewer reactions. Thus, we believe the intervention does not incur any greater distress than usual ACP practices.

Second, data collection also conforms with the definition of minimal risk. No direct input from the resident or family member is needed to obtain any data for this study. All the data are already being collected as part of routine medical care (EMR, MDS, Medicare data). The only additional data being collected in the intervention NHs is the Video Status Report User Defined Assessment, which is being embedded into the EMR. The Video Status Report User Defined Assessment is needed to monitor intervention fidelity and will be incorporated into the intervention facility’s ACP protocol.

7.2. Serious Negative Reactions and Serious Adverse Events

The potential *serious negative reaction (SNR)* that could occur during this trial is serious distress by patients or family members in the intervention NHs while viewing an ACP video. As described in *Section 7.1.*, we anticipate that such SNRs will be exceedingly rare. Nonetheless, serious distress by may be manifested as a very negative emotional reaction while watching or after watching a video, asking for the video to be stopped, or leaving the room while a video is being shown. Due to the sensitive nature of the material, tearing up by the proxy can be expected and is not deemed to be a reflection of distress.

We do not believe that there are any potential consequences of this trial that meet the definition of *serious adverse events (SAEs)*.

(We do not believe death should be considered a SAE for the PROVEN trial for the following reasons. First, the study is being conducted in a frail NH population with advanced illnesses. Thus,

death is often not an unexpected event in their clinical course. Second, all NHs must engage patients and families in ACP as part of routine clinical practice. The videos are meant as an adjunct to facilitate ACP counseling. The underlying intent of all ACP, regardless of how it is done, is to help patients make informed treatment decisions so they receive care that is concordant with their preferences. For patients who prefer comfort or palliation as a main goal of care (vs. life prolongation), death is not an adverse outcome. Finally, it is not known whether more aggressive care (i.e., hospitalization) would result in greater mortality compared to less aggressive care (i.e., conservative or palliative treatment on-site in the NH). Therefore, while we hypothesize that there will be fewer hospitalizations among NH patients with advanced disease randomized to the intervention arm (vs. control), it is impossible to predict how this may impact mortality rates.)

7.3. Reporting Procedures

As part of NH staff training, instructions will be given to the facility ACP Champions and providers who will be showing the video (i.e., physician, nurse, social worker) about what constitutes an SNR, i.e., serious distress by a patient or family member during or immediately after a video. As described in *Section 7.1.*, we anticipate that such SNRs will be exceedingly rare. Nonetheless, staff will be instructed that if such an event occurs, then the video should be stopped. The provider should report the event to his/her immediate supervisor and ACP Champions as soon as possible, but not exceeding 4 hours after the event. Together, these health professionals will determine the severity of the event. If deemed to be a true SNR, the ACP Champion will complete an SNR Form created by our research team, which will be submitted to the research project directors via email or fax within 24 hours of the event. The ACP Champion will also inform the PROVEN project director within 24 hours of the event by telephone. The project director will report the SNR to all 3 co-PIs via email or telephone immediately upon becoming aware of the event and will also notify the Data Safety and Monitoring (DSMB) Chair in writing (email and hard copy) within 48 hours. It will ultimately be the co-PIs responsibility to ensure that the DSMB chair is informed in a timely manner. The Brown University IRB has indicated that SNRs do not need to be reported to them. This is because the video intervention itself is considered standard operating procedures in the nursing homes, and so it is not part of the human subjects research that the IRB is monitoring.

7.4. Follow-up for Serious Negative Reactions

The NH provider and ACP Champion will be instructed to check on the patient or family who experienced the distress at 6 and 24 hours after a SNR to see how he/she is managing. If deemed necessary, a patient should be referred for counseling with a NH social worker or other mental health professional. In the case of a family member, if deemed necessary, the NH provider may suggest to the proxy that he/she contact his/her own primary care provider. The research project director will contact the facility ACP Champion within 48 hours of the SNR to determine the status of the patient/family and whether further counseling was deemed necessary. The project director will in turn report the follow-up information to the co-PIs (by telephone) and to the DSMB (in writing) within 72 hours using an SNR Follow-up form.

8. INTERVENTION DISCONTINUATION

The study may be discontinued at any time by the IRB, the NIA, the OHRP, the FDA, or other government agencies as part of their duties to ensure that research participants are protected. Individual NHs in the intervention arm may withdraw from study participation at any time at the discretion of their senior management or corporate supervisors. Individual patients and families, while not being asked to provide informed consent for this research, can refuse to watch a video offered to them as part of this new ACP video program being adopted into the clinical practice of participating intervention NHs. Such refusals are expected as part of this pragmatic trial.

9. STATISTICAL CONSIDERATIONS

9.1. General Design Issues

PROVEN is pragmatic cluster RCT of an ACP Video Program intervention for NH patients cared for in two NH health care systems: Genesis HealthCare and PruittHealth. Rationale for this choice of study design is provided in Section 2.6. The intervention will be implemented facility-wide; thus, all patients in the NHs during the 24-month implementation period comprise the study population. However, the analytic plan focuses on the effect of the ACP Video Program vs. control in the following targeted patient sub-groups:

- Long-stay residents (≥ 90 days) with advanced dementia or advanced CHF/COPD (Aim 2)
- Short-stay patients (< 90 days) with advanced dementia or advanced CHF/COPD (Aim 3)
- Long and short-stay patients without these advanced illnesses (Aim 4).

The primary trial outcome is hospital transfers (number of hospital transfers/person-days alive based on Medicare claims data), which include admissions, emergency department visits, and observation stays over a 12-month follow-up period among Medicare fee-for-service long-stay residents with advanced dementia or advanced CHF/COPD. The primary hypothesis is that the rate of hospital transfers will be lower in the intervention group.

Secondary outcomes include hospital transfer rates in the sub-groups examined in Aims 3 and 4, and the following outcomes for all sub-groups in Aims 2, 3 and 4: advance directives, burdensome treatments, hospice use, and Medicare ACP billing codes.

Each long-stay resident will be followed for up to 12 months starting from the date they are first identified as meeting our target cohort definition during the 24-month intervention period and short-stay patients will be followed for 100 days from their NH admission date. The analytic approach to Aims 2, 3, and 4 are similar. Analyses begin with descriptions of all major variables using frequencies and means/medians with SDs/interquartile ranges, as appropriate. Outcomes will be compared between the control and intervention arms using a zero-inflated Poisson model

with random effects to account for clustering at the NH level. While we do not anticipate an effect on mortality, analyses will also examine the effects on mortality. Primary analyses will follow the intention to treat principle and will adjust for minor imbalances in patient characteristics, as needed.

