4. *Decisions about Hospice*
5. *General Information about Advance Care Planning for Healthy Adults*

NHs randomized to the control arm of the study will use the usual ACP procedures already practiced in their facilities. The ACP Video Program will be implemented for 24 months in the intervention facilities. Individual patients in both arms who are in the NHs during the 24-month implementation period are eligible, and their outcomes will be assessed for up to 12 months in the long-stay cohort and 100 days in the short-stay cohort.

Sample Size and Population: The ACP video intervention will be implemented facility-wide in the NHs randomized to the intervention arm. Thus, ALL patients who are cared for during the 24-month implementation phase are potential participants in the trial and comprise the study population ($N \simeq 152,160$). However, the analyses described in Aims 2 and 3 will focus on target populations with advanced comorbid conditions that are cared for in the NHs during the 24-month implementation period. For Aim 2, the target sample is long-stay patients with advanced dementia or CHF/COPD ($N \simeq 14,760$). As the primary study trial outcome is hospital transfers in the long-stay patients, sample size estimates and power calculations are based on this target group. For Aim 3, the target sample is short-stay patients with advanced dementia or CHF/COPD. For Aim 4, the target sample is long-stay and short-stay NH patients who do NOT have either of the pre-specified advanced illnesses.

In this stratified cluster RCT, the unit of random assignment is the facility. Facilities will be randomized in the following strata in the following order: 1. Health care system (Genesis HealthCare and PruittHealth), and 2. Hospitalization rates in the 12 months prior to recruitment in target sub-populations (grouped as terciles). Outcomes analyses will not differ by strata.

STUDY TEAM ROSTER

Co-Principal Investigators:

[name], MPH

Senior Scientist, Institute for Aging Research, Hebrew SeniorLife,

Professor of Medicine, Harvard Medical School

<http://www.instituteforagingresearch.org/>

Address: [name]

[contact], [contact]

Email: [contact]

Main Roles: Member of Steering and Executive Committees; leader of Human Subjects and Data Safety and also Stakeholder Engagement working groups; management of team that coordinates all intervention implementation and training activities.

[name]

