randomized to the control arm, and 3. Our partner health care systems strongly preferred post-randomization recruitment.

Once the intervention NHs are recruited, intervention training and implementation will be rolled out in a staggered fashion over the next 6 months (*see Section 5.2*), such that by month 8 of year 1, all intervention NHs will be up and running.

[figure not shown]
4.4.2. Facility Recruitment Estimates:

Based upon our sample size calculations, we require 103 facilities per arm (See section 9.2). To account for the fact that some (we estimated up to 10%) facilities randomized to the intervention arm would fail to participate fully in the intervention implementation (but will be included in our intention to treat analysis) we increased our facility recruitment targets by at least 10%, for a total of 119 facilities in the intervention study arm.

From the pool of eligible facilities, 119 will be randomly assigned to the intervention arm, and all the remaining eligible facilities (n=241) will be assigned to the control arm (approximate 2:1 control:intervention match). We will leave all non-intervention facilities in the control arm since there is no additional cost to do so and having the increased number of control facilities increased precision.

4.4.3. Facility Randomization and Stratification Procedures:

Facilities will be randomized using a stratified approach with two levels of stratification. The first stratum is the NH health care system (Genesis HealthCare and PruittHealth). Within each health system, the second stratum will be on the hospitalization rate as measured by # hospitalization/person-days alive for patients with advanced dementia or COPD/CHF in all NHs in each health care system in the prior 12 months based on MDS files available at Brown University. The rationale for this stratum is that hospitalization rates, the primary trial outcome, are known to vary considerably at the facility-level due to regional practice, market influences and underlying quality. Since inter-facility hospitalization rates vary quite broadly, facilities will be grouped into terciles to minimize the chance of misdistribution. After the second stratification level is applied, facilities will be randomly assigned to either the control or intervention arm by a statistician at Brown University. Immediately following random assignment, we will test the balance between the arms using all available facility and resident-level data.

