Data for 2012-13 from our partners reveal that there are, on average, 42 people meeting advanced dementia and/or CHF/COPD target criteria per facility. Thus, we estimate that there will be approximately 4,326 target patients in the 103 control NHs in (103*42=4,326) required by our aforementioned power calculation. In the actual assigned facilities, we estimate there will be 4998 patients meeting these criteria in 119 intervention NHs and 10,122 patients in the 241 control NHs.

9.2.2. Treatment Assignment Procedures: Please refer to *section 4* for a detailed description of the treatment assignment procedures.

9.2.3. Blinding: Our partner health care systems will know which facilities are designated intervention facilities, but will not be aware of those in the control group. Only Brown University statistician and data management staff will know the identity of the control facilities. They will present aggregated post-random assignment comparisons of intervention and control facilities' baseline characteristics, but these preliminary analyses will be not generated at the individual facility level. As [name] will be leading intervention training, he will be aware of the identity of the intervention NHs but will not be involved in data analyses activities. Drs. [name] and [name] will be blinded to the identity of both the control and intervention facilities. Facility assignment will be unblinded to the DSMB members at their request.

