Using current MDS data from CMS, we observe that the distribution of the primary outcome, hospital transfers, is over-dispersed with many of the patients having no hospital transfer over the 12-month follow up period. In addition, we also observed that hospital transfer rates vary across facilities, even after adjusting for underlying patient risk. To account for these phenomena, we will utilize a zero-inflated Poisson distribution with facility random effects to test and estimate the effects of the ACP intervention. Zero-inflated Poisson models have been used in other public health settings.^{128, 129} Formally, let Y_{ij} be the number of hospital transfers for person i in facility j , N_{ij} is the number of person days alive for person i in facility j , and T_j is a treatment indicator that is equal to one if facility j is in the intervention group. Then where β_1 is the conditional increase in the log hospital transfer rate in facilities that receive treatment vs. those that do not, and α_1 is the conditional log odds ratio for being hospitalized vs. never being hospitalized in the intervention vs. the control arm. When both α_1 and β_1 are smaller than 0, the ACP video is effective in reducing the proportion of patients hospitalized and the number of times hospitalized. Using this model we will estimate the marginal average hospital transfer rate in each arm and calculate the difference between the two arms. We will use a two sided test to examine if the marginal average difference is significantly different than zero, and we will calculate the corresponding interval estimate. As a secondary analysis, we will use the likelihood ratio test to compare the null hypothesis, $H_0 : \alpha_1 = \beta_1 = 0$, to the alternative hypothesis $H_1 : \alpha_1 \neq 0$ or $\beta_1 \neq 0$.¹³⁰ Confidence intervals for α_1 and β_1 can be obtained by inverting the likelihood ratio test.¹³² This analysis will enable us to provide additional details as to whether the effectiveness of the intervention is to reduce the likelihood of one hospital transfer or the number of hospital transfers if transferred at least once.

The secondary outcomes are binary. Commonly used methods applied to the analysis of clustered RCT with binary outcomes are GEE and multilevel models.¹³¹ The former method provides a population “average” effect, while the latter results in a conditional cluster effect. For continuous Gaussian data, interpretation of the treatment coefficient

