$$\begin{aligned}
 p(Y_{ij} = 0) &= \phi_{ij} + (1 - \phi_{ij}) \exp^{-\theta_{ij}} \\
 P(Y_{ij} = y) &= (1 - \phi_{ij}) \frac{\exp^{-\theta_{ij}} \theta_{ij}^y}{y!} \quad y = 1, 2, \dots \\
 \text{logit}(\phi_{ij}) &= \alpha_0 + \alpha_1 T_j + u_j \quad u_j \sim N(0, \sigma_u^2) \\
 \text{log}(\theta_{ij}) &= \beta_0 + \beta_1 T_j + \log(N_{ij}) + v_j \quad v_j \sim N(0, \sigma_v^2)
 \end{aligned}$$

is the same in conditional and marginal models; however, with binary data, the treatment coefficient from a marginal model is smaller than that from a conditional model and has a different interpretation.¹³² For binary outcomes, Bellamy et al¹³³ have shown that with few clusters GEE results were more likely to reject the null hypothesis, while conditional models resulted in more conservative estimates. Austin concluded that the power of GEE and multilevel models are very similar for studies, like ours, that include more than 30 clusters (facilities) with either variable or equal cluster size.¹³⁴ To estimate the effect of ACP on secondary outcomes we will use random effects logistic model. Formally, let S_{ij} one of the secondary outcomes for person i in facility j , and T_j is a treatment indicator that is equal to one if facility j is in the treated arm.

$$\begin{aligned}
 S_{ij} &\sim \text{Ber}(p_{ij}) \\
 \text{logit}(p_{ij}) &= \gamma_0 + \gamma_1 T_j + \zeta_j \\
 \zeta_j &\sim N(0, \sigma_\zeta^2)
 \end{aligned}$$

where γ_1 is the conditional log odds ratio for observing the secondary outcome in the treatment arm vs. the control arm. When γ_1 is smaller than 0, ACP is effective. As for the primary outcome we will use the likelihood ratio test the null hypothesis $H_0 : \gamma_1 = 0$, and by inverting this test we will obtain the corresponding confidence interval.

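### The primary model leaves out the randomization strata and the facility's prior-year hospitalization rate, and adjusts only for patient characteristics if imbalance appears

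*Combined protocol and SAP*

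**What the plan says.** Section 9.1 states: "Primary analyses will follow the intention to treat principle and will adjust for minor imbalances in patient characteristics, as needed". It gives no covariate list, no threshold for imbalance and no time at which the choice is made.

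For Aim 2, section 9.5 says "we will utilize a zero-inflated Poisson distribution with facility random effects to test and estimate the effects of the ACP intervention". The log rate is written as "\beta_0 + \beta_1 T_j + \log(N_{ij}) + v_j", and the zero part has the same form without the offset. Neither part contains a resident covariate, a facility covariate or a stratum term. The Précis adds: "Outcomes analyses will not differ by strata".

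Section 4.4.3 stratifies the randomization by health system and then by terciles of the facility's prior-12-month hospitalization rate in the target population. The reason given is that facilities differ widely on this rate. Section 6.3.1 confirms the source: "MDS data are also used to calculate the hospitalization rate of each facility". Table 2 lists the purpose of this rate as randomization only and keeps the covariate label for patient-level items. Section 6.3.1 also says claims will be used to obtain facility "hospitalization rates for the subset of patients with Medicare fee for service".

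After allocation, section 4.4.3 says: "Immediately following random assignment, we will test the balance between the arms using all available facility and resident-level data". Nothing links the result of that check to the model. Facility covariates appear only in the supplemental as-treated models of section 9.6. The Aim 4 model has covariates, but they are not named.

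**The concern.** In a randomized trial a covariate earns its place by predicting the outcome, not by being out of balance. The plan does the reverse: imbalance is the trigger, and only patient characteristics are eligible. Section 9.5 itself observes that transfer rates differ between facilities even after allowing for patient risk, so patient covariates cannot remove that variation. The plan's one purpose-built measure of it, the prior facility rate, is spent on allocation and then dropped.

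Two things follow. First, when randomization is stratified on a predictor and the analysis ignores the strata, the estimate is more stable than its reported standard error says, so intervals are too wide and the test is conservative. Second, the information in the rate beyond its terciles goes unused. The open wording also leaves the content of the primary model unsettled: the resident cohort accrues over 24 months, so the imbalance section 9.1 refers to cannot be fully known at randomization.

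**Working it through.** **Inputs.** From section 9.2: control rate 1.51 per person-year, reduction 0.25 (to 1.26), 90% power, 103 facilities per arm, 42 target residents per facility, 119 and 241 facilities assigned. From section 9.5: a two-sided test. Assumed: alpha 5%, 42 person-years per facility, Poisson counts within a facility. Not stated: the between-facility coefficient of variation k, and the share R² of between-facility variance that the prior rate explains (30-50% assumed).

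**The plan's figure.** The usual cluster formula for two incidence rates is c = 1 + (1.960 + 1.2816)² × [(λ0 + λ1)/y + k²(λ0² + λ1²)] / (λ0 − λ1)².

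Setting c = 103: 102 × 0.0625 / 10.507 = 0.6067. Subtracting 2.77/42 = 0.0660 leaves 0.5408. Dividing by 1.51² + 1.26² = 3.8677 gives k² = 0.1398, so k = 0.374. This k matches all eight cells of the 1.06 and 1.51 rows. For the 2.12 row it gives 326.7, 255.5, 204.8 and 167.6 against the printed 351, 275, 220 and 180; that row needs k = 0.389. So k is back-solved and agrees with two of the three rows. The third row is not an error on this evidence, since k may differ by row.

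**Where the variance lies.** In a control facility the between-facility part is 0.1398 × 1.51² = 0.319 and the Poisson part is 1.51/42 = 0.036, a between-facility share of about 0.90. A facility-level predictor therefore acts on the larger component.

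**Standard error at 119:241.** SE² = [λ0/y + k²(1 − R²)λ0²]/241 + [λ1/y + k²(1 − R²)λ1²]/119. With R² = 0 this is 0.3547/241 + 0.2520/119, so SE = 0.0599. Terciles of a normal predictor keep (2/3) × 1.091² = 0.79 of its R².

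| R² (assumed) | No covariate | Tercile terms | Continuous rate |
|---|---|---|---|
| 0 | 0.0599 | 0.0599 | 0.0599 |
| 0.30 | 0.0599 | 0.0532 | 0.0513 |
| 0.50 | 0.0599 | 0.0482 | 0.0447 |

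Against no covariate, the continuous rate lowers the SE by 1 − 0.0513/0.0599 = 14% and 1 − 0.0447/0.0599 = 25%. Against tercile terms it is lower by 1 − 0.0513/0.0532 = 4% and 1 − 0.0447/0.0482 = 7%.

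**Sensitivity.** The ratio of SEs is roughly √(1 − share × R²). Over both arms the between-facility share is 0.5408/0.6067 = 0.89. With total variance held fixed, 21 person-years per facility and two-fold over-dispersion together would multiply the Poisson part by four: 1 − 4 × 0.0660/0.6067 = 0.57 (rounded up). The reductions then become 1 − √(1 − 0.57 × 0.30) = 9% and 1 − √(1 − 0.57 × 0.50) = 15%.

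**Does the unadjusted model credit the stratification?** A simulation used 360 facilities, k = 0.374, tercile-stratified 119:241 allocation, no true effect and 1,500 runs per setting. Facility rates were analysed by linear regression with robust standard errors. This stands in for the zero-inflated model, and the prior rate was the same measure as the outcome one year earlier.

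| Year-to-year correlation | True SD, unadjusted | Reported SE, unadjusted | Rejection, unadjusted | Reported SE, terciles | Reported SE, terciles + continuous |
|---|---|---|---|---|---|
| 0 | 0.065 | 0.067 | 3.9% | 0.067 | 0.067 |
| 0.5 | 0.062 | 0.067 | 4.1% | 0.062 | 0.060 |
| 0.7 | 0.055 | 0.067 | 1.9% | 0.056 | 0.052 |
| 0.8 | 0.054 | 0.067 | 1.9% | 0.053 | 0.047 |

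At correlation 0.7 the unadjusted reported SE is 0.0665/0.0553 = 1.20 times the true one. Tercile terms correct this; the continuous rate adds a little more.

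**Power.** By formula at 119:241, power for a 0.25 reduction is 98.7% with no covariate. For an illustrative halved effect of 0.125 it is 51% with R² = 0, 61% with 0.25 and 76% with 0.50. In the simulation at correlation 0.7, power for 0.125 was 49% unadjusted, 63% with terciles and 68% with the continuous rate added.

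**The case against.** The best defence is that the prior rate is already in the design. Stratifying on terciles buys part of the precision, and most of the fall in reported SE is credit for that; the further gain from the continuous rate is 4-7%. The stratifier is an MDS hospitalization rate while the outcome is claims-based transfers, including emergency visits and observation stays, so the correlation may be modest. At the planned effect the trial has power to spare. All of this stands and limits the size. It does not justify a model without the strata. Facility random effects handle clustering, but they do not credit variation that a known baseline rate would explain.

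The Précis sentence on strata could mean only that no separate analyses by stratum are planned. That is a fair reading, but the model as written still has no stratum term.

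Extra resident covariates also have a cost. Function and cognition largely define the target conditions, and for incident cases they are measured after implementation starts.

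Three stronger readings are tempting and not supported:

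- A reader might infer that the prior rate plays no part in the trial. It does, through allocation; it is missing from the primary model only.
- A reader might infer that someone who knows the allocation will pick the adjusted or unadjusted result after seeing both, raising the false-positive rate. Section 9.2.3 says "Only Brown University statistician and data management staff will know the identity of the control facilities", which tells us who knows the allocation, not who decides on adjustment. The balance check comes straight after allocation, before outcomes exist, and no passage plans two competing tests.
- A reader might infer that a claims-based transfer rate for the target group is ready to use. The claims sentence in section 6.3.1 concerns hospitalizations and names neither the target group nor the period.

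**Conclusion.** The point holds as a matter of efficiency and pre-specification. The primary model ignores a stratifier chosen because facilities differ on it, and the adjustment rule confines covariates to patient characteristics. The reported interval will be wider than it need be to the extent that the prior rate predicts transfers.

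How much wider cannot be settled from the documents. The range given rests on the back-solved k, 42 person-years, Poisson counts and an assumed R²; lower person-years or over-dispersion shrink it, and zero correlation removes it. This is not a power failure at the planned effect. It matters because section 9.6 reports that only 12.5% and 31.4% of long-stay residents in the two systems had been shown a video, so a diluted effect is a real prospect. Precision would then decide how informative a null result is.

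**What to change.** Replace the sentence in section 9.1 with a rule of this kind: whatever the observed balance, the primary model includes health system, prior-rate tercile and the continuous prior-year facility rate, plus a short fixed list of resident covariates at cohort entry, chosen before outcomes are examined. The continuous rate can be the MDS rate already held, or a claims-based fee-for-service version if one is built. Prefer resident covariates that neither restate the cohort definition nor could be altered by the program, such as age and sex.

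Add the terms to both parts of the Aim 2 model and obtain each arm's marginal rate by standardising over them. State that balance tables are descriptive and do not change the model. Report the unadjusted result as a sensitivity analysis. Add a purpose of covariate for the prior rate in Table 2, and reword the Précis sentence on strata so that it does not conflict.

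The cost is SAP wording and, for the MDS version, no new data. The downsides are a few more parameters in a two-part model with two random effects, and a noisy baseline rate in facilities with few eligible residents, where shrinkage toward the mean would help.
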